11.7.3.4.2. Sites

Participating study sites will:

- Extract, transform, and load (ETL) data into a physical instance of an adapted PCORnet Common Data Model. Sites will document the mapping from the EHR to the Common Data Model.
- Install PopMedNet
- Refresh the Cohort DataMart on a biweekly basis
- Execute data characterization and test queries after each refresh and on an as-needed basis.

Site study coordinators will be required to complete pre-screening logs on all potential study participants meeting minimum eligibility requirements (age >40, Type 2 diabetes, established cardiovascular disease) identified via any mechanism (i.e., reviewing lists of scheduled office patients, reviewing lists of recently discharged diabetes patients, EHR-facilitated algorithm). Pre-screening logs will capture the following information:

- Pre-screening number
- Pre-screening date
- Inclusion criteria not met
- Exclusion criteria met
- Other criteria

Site study coordinators will complete a screening survey which will describe the site's current process for screening. A description of screening barriers will be included.

11.7.4. DATA ANALYSIS

11.7.4.1. Sample Size Expectations

The objectives of this ancillary study are exploratory (not confirmatory) in nature and not intended to be sufficiently powered to confirm a pre-determined level of sensitivity and specificity. The number of sites and subjects that will participate in the ancillary study depends upon the outcome of the site EHR capabilities assessment described in Section 11.7.3.2 (Site Selection). Five study sites recruiting 12-15 subjects each would enable a descriptive assessment of Objectives 1 and 2, whilst, if feasible, 500-1000 subjects at EHR-enabled sites would permit greater precision to be achieved in the assessment of Objective 3.

11.7.4.2. Objective 1: Assess the Barriers to Using as EHR-Generated List of Patients to Facilitate Trial Enrollment

Because any survey administered for this objective will be a site-level survey, analysis of the survey data will be performed across all sites. For quantities of interest, frequencies with percentages for categorical measures and means with standard deviations for continuous measures will be presented.

11.7.4.3. General Analytic Approach for Objective 1 and Objective 2

The goals of both Objective 2 and Objective 3 involve evaluating the performance of algorithms that map EHR-based data into concepts present in the clinical trial dataset. The actual measures recorded in the clinical trial dataset will be considered the reference standard against which these algorithm-based measures are compared.

Table 4 Overall performance of EHR-based algorithms for baseline characteristics, using clinical trial data as the reference standard / Categorical variables

| New measure (EHR Ancillary Study data) | Reference standard (Clinical trial data) | |
|---|---|------------------------|
| | Condition present | Condition absent |
| Condition present | True positive (TP) | False positive (FP) |
| Condition absent | False negative (FN) | True negative (TN) |

For categorical variables, estimated performance metrics will be based on the 2x2 cross-tabulation of values in the EHR Ancillary Study dataset with values in the clinical trial dataset (Table 4) and include:

- Overall agreement = $(TP + TN) / (TP + FP + FN + TN)$
- Sensitivity = $TP / (TP + FN)$

- Specificity = $TN / (FP + TN)$
- Positive predictive value = $TP / (TP + FP)$
- Negative predictive value = $TN / (FN + TN)$
- Accuracy or efficiency = $(TP + TN) / (TP+TN+FP+FN)$

For dichotomous measures, each of these proportions is immediately calculable. For measures having more than two levels, multiple dichotomous measures will be created in order to calculate these proportions. Confidence intervals (95%) will be reported around these quantities. (See [Table 5](#) as an example).

Table 5 Overall performance of EHR-based algorithms for baseline characteristics, using clinical trial data as the reference standard / Categorical variables

| Measure | Overall agreement (95% CI) | Sensitivity (95% CI) | Specificity (95% CI) | Positive predictive value (95% CI) | Negative predictive value (95% CI) |
|-----------|----------------------------|-----------------------|-----------------------|------------------------------------|------------------------------------|
| Measure 1 | xx.x (xx.x – xx.x) | xx.x (xx.x – xx.x) | xx.x (xx.x – xx.x) | xx.x (xx.x – xx.x) | xx.x (xx.x – xx.x) |
| Measure 2 | xx.x (xx.x – xx.x) | xx.x (xx.x – xx.x) | xx.x (xx.x – xx.x) | xx.x (xx.x – xx.x) | xx.x (xx.x – xx.x) |
| | | | | | |

Reported on 0–100 scale

For continuous measures, bias will be calculated as the difference between values in the EHR Ancillary Study dataset and values in the clinical trial dataset. The mean and standard deviation of the bias along with a 95% confidence interval will be reported. In Bland-Altman analyses of agreement between continuous measures, the standard deviation of the bias is referred to as the precision, while the 95% confidence interval is referred to as the limit of agreement. (See [Table 6](#) as an example).

Table 6 Overall performance of EHR-based algorithms for baseline characteristics, using clinical trial data as the reference standard / Continuous variables

| Measure | Bias | |
|-----------|-----------|----------|
| | Mean (SD) | 95% (CI) |
| Measure 1 | xx.x | xx.x |
| Measure 2 | xx.x | xx.x |
| | | |

Due to the nature of EHR data, it is expected that there will be systematic differences between sites with respect to coding of clinical concepts. All performance metrics will therefore initially be calculated by site. These site-specific results may be best reported graphically.

There is also interest in an assessment of algorithm performance across all sites. Hierarchical models will be used to combine data from all sites and estimate performance at the “average” site. To estimate proportions (e.g. for overall agreement, sensitivity, specificity, etc. associated with categorical measures), models will be specified as:

$$\begin{aligned} \text{logit}(E(y)) &= \beta_0 + \gamma_{0,j} \\ \gamma_{0,j} &\sim N(0, s^2) \end{aligned}$$

where sites are indexed by j . The value of the proportion at the average site—when $\gamma_0=0$ —is $[1 + \exp(-\beta_0)]^{-1}$. Patients included in the estimation of each model vary by performance metric and reflect the definitions above. As an example, consider positive predictive value. To estimate the positive predictive value of an algorithm, only subjects with true positive value and false positive values will be included. True positives will be assigned $Y=1$ and false positive will be assigned $Y=0$.

To estimate means (e.g. for bias associated with continuous variables), the model will be specified as:

$$\begin{aligned} E(y) &= \beta_0 + \gamma_{0,j} \\ \gamma_{0,j} &\sim N(0, s^2) \end{aligned}$$

The value of the mean at the average site is β_0 .

For all models, we will assess site heterogeneity by testing if $s^2=0$.

11.7.4.4. Objective 2: Evaluate the Fitness of EHR Data for Use in Populating the Baseline Characteristics in the eCRF

Algorithms will be defined to map EHR-based data in the Study Data Mart to specific concepts in the EHR Ancillary Study dataset that parallel concepts in the clinical trial dataset. For Objective 2, the performance of algorithms used to identify baseline characteristics will be evaluated. The baseline characteristic measures recorded in the clinical trial dataset will be considered the reference standard against which these algorithm-based measures are compared.

11.7.4.5. Objective 3: Explore the Use of EHR Data to Find Events of Interest During Trial Follow-up

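### Section 11.7.4.3 of the EHR ancillary study equates the 95% confidence interval of the bias with the Bland-Altman limits of agreement, which are a different and wider interval

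*Protocol*

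**What the plan says.** Appendix 7, Section 11.7.4.3, defines bias for a continuous measure as the EHR value minus the clinical trial value. It then states: "The mean and standard deviation of the bias along with a 95% confidence interval will be reported". The next sentence ties this to Bland-Altman terms: "the standard deviation of the bias is referred to as the precision", "while the 95% confidence interval is referred to as the limit of agreement".

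The example layout, Table 6, is captioned "Overall performance of EHR-based algorithms for baseline characteristics, using clinical trial data as the reference standard / Continuous variables". Under the heading of bias it has a column for mean (SD) and a column for the 95% CI. It has none for limits of agreement. The same sentence and layout appear in the Amendment 1 and original protocol texts, where the table is numbered 5.

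On the level of analysis, the section says: "All performance metrics will therefore initially be calculated by site". It then adds: "Hierarchical models will be used to combine data from all sites and estimate performance at the “average” site". For continuous variables that model has a random site intercept, and its target is the mean at the average site.

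On size, Section 11.7.4.1 says: "Five study sites recruiting 12-15 subjects each would enable a descriptive assessment of Objectives 1 and 2". It also says that, if feasible, "500-1000 subjects at EHR-enabled sites would permit greater precision to be achieved in the assessment of Objective 3".

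**The concern.** A confidence interval for a mean difference and the limits of agreement answer different questions. The first says how well the average difference is known, and its width goes to zero as subjects are added. The second says how far a single EHR value may plausibly lie from the corresponding eCRF value, and its width does not depend on the sample size except through estimation error.

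Objective 2 concerns whether EHR data are fit to fill baseline fields of the eCRF. Those fields hold one value per subject, so the spread of individual differences is the relevant quantity. A mean bias near zero with a narrow confidence interval can coexist with large individual discrepancies. An analyst who follows the sentence literally would present the confidence interval as the agreement result and understate that spread.

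**Working it through.** The protocol gives no interval width for this analysis, so there is no stated figure to reproduce. The check compares the two half-widths.

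**Inputs.** Sections 11.7.4.1 and 11.7.4.3 give five sites of 12 to 15 subjects for Objectives 1 and 2, hence 5 × 12 = 60 to 5 × 15 = 75 subjects; by-site calculation first; then a random-site model. The intraclass correlation (ICC) between subjects of the same site is not given. It is assumed here at 0.05 to 0.2.

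**Formulas.** With SD the standard deviation of the differences:
- half-width of the 95% CI of the mean = 1.96 × SD/√n
- half-width of the limits of agreement = 1.96 × SD
- ratio = √n, whatever the SD

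**By site.**
- n = 12: √12 = 3.46
- n = 15: √15 = 3.87
- With a t-based confidence interval the ratios are 3.08 and 3.54.

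**Pooled, ignoring site.**
- n = 60: √60 = 7.75
- n = 75: √75 = 8.66
- With a t-based confidence interval the ratios are 7.59 and 8.52.

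**Pooled with the random-site model.** Set the total SD to 1, with J sites of m subjects. Then SE² = ICC/J + (1 − ICC)/(J × m), and the ratio is 1/SE.
- J = 5, m = 12, ICC 0.05: SE² = 0.0100 + 0.0158 = 0.0258, ratio 6.22
- J = 5, m = 12, ICC 0.2: SE² = 0.0400 + 0.0133 = 0.0533, ratio 4.33
- J = 5, m = 15, ICC 0.05: ratio 6.64
- J = 5, m = 15, ICC 0.2: ratio 4.44

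The range over these assumptions is about 4.3 to 6.6.

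**Coverage.** Take normally distributed differences and an interval centred on the true bias. The share of individual differences inside the confidence interval of the mean is 2Φ(1.96/√n) − 1:
- n = 12: 43%; n = 15: 39%
- n = 60: 20%; n = 75: 18%

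Limits of agreement should contain about 95%.

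**The case against.** **The label may be the only error.** No formula is written, the sentence does not say that the interval is that of the mean, and bias is defined on individual values. The authors may have meant mean ± 1.96 SD and named it badly, in which case nothing would be too narrow. This reading is possible, so it cannot be said that agreement will be overstated, only that it would be if the text is followed literally. It does not rescue the text. Elsewhere in the same section, 95% confidence intervals express uncertainty around estimated proportions, and the pooled model estimates only a mean. The label would need correcting in any case.

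**The SD is shown beside the mean.** This stands. A reader who knows the method can compute the simple limits, so the individual spread is not hidden. It is less help for the pooled result, for which the section defines no total SD.

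**A reader might infer a factor of 22 to 32**, from √500 = 22.4 and √1000 = 31.6. The documents do not support that as the expected size. The 500 to 1000 subjects are named for Objective 3, for which Section 11.7.4.5 names only sensitivity and positive predictive value and no continuous bias. Footnote 3 to the objectives table in Section 2 (Amendment 1 text) places the event and baseline comparisons in the same data subset, so a larger Objective 2 sample is conceivable. Even then, the factor requires that site differences be ignored, and the section expects systematic ones.

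**A reader might also infer that unfit variables would be passed as interchangeable.** Appendix 7 contains no acceptance threshold and no rule of that kind. Objective 2 is a descriptive assessment of agreement.

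**The study is exploratory and the table is only an example.** Both are true. Details of layout can be left to an analysis plan. A sentence that gives a standard term the wrong meaning is a different matter, because an analysis plan written from it would carry the error forward.

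**Conclusion.** The point holds as an error of definition. Section 11.7.4.3 equates two intervals that differ by a factor of √n for independent observations, and the example table has no place for the right one.

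If the confidence interval of the mean is reported as the limits of agreement, continuous baseline variables would look about 3.5 to 3.9 times too closely matched by site (3.1 to 3.5 with a t-based interval). With 60 to 75 subjects pooled ignoring site, the factor is about 7.7 to 8.7. Under the planned random-site model it is about 4.3 to 6.6 for an assumed ICC of 0.05 to 0.2. It would be larger only if more subjects contribute to the baseline comparison.

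Severity is low. The ancillary study is exploratory and reported separately from the main study report, and the MACE analysis does not depend on it.

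**What to change.** Replace the Bland-Altman sentence in Section 11.7.4.3 by: *Limits of agreement are mean bias ± 1.96 SD of the differences, reported with the mean bias and its 95% CI.*

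Give Table 6 separate columns for mean bias (95% CI), SD of the differences, and limits of agreement.

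For results combined across sites, base the limits on the total variance: β0 ± 1.96 × √(between-site variance + within-site variance). The section at present names only the between-site term s², so the within-site residual variance should be defined with it.

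The cost is a short wording change in Appendix 7 and a revised table layout, with no new data. If the confidence interval of the mean would otherwise have been shown, the reported agreement will look less favourable.

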11.8. Appendix 8: Country Specific Requirements

11.9. Appendix 9: Protocol Amendment Changes

11.9.1. Changes Resulting from Protocol Amendment 1

This amendment is applicable to all participating countries.

Summary of Changes

1. Correction of typographical error in Exclusion criterion 7.
2. Clarification wording added to the description of when subjects should have telephone follow-up after discontinuing investigational product (IP). Subjects should have the telephone follow-up 5 ± 1 weeks after their last dose of IP whether they had continued IP through to the Final study visit, or discontinued before the Final study visit.
3. Time and Event Table modified to add adverse event checking (SAE, AEs of special interest, AEs leading to IP discontinuation) to dose adjustment visits, and to correct footnote assignment/typographical errors.
4. Revision of terminology used to describe unstable angina events referred for CEC adjudication to correctly reflect review process to be adopted by CEC.
5. Addition of Country Specific Requirements appendix (Appendix 8).

List of Specific Changes

Section 4.2, Exclusion criteria; criterion 7, fourth sentence.

Original text:

Women who have developed spontaneous secondary amenorrhoea of 12 months or more where post-menopausal status is in doubt, a blood sample where FSH >40MU/ml and oestrodiol <40 pg/mL (<14 pmol/L) are simultaneously measured will be considered confirmatory.

Amended text:

Women who have developed spontaneous secondary amenorrhoea of 12 months or more where post-menopausal status is in doubt, a blood sample where FSH >40MU/ml and oestrodiol <40 pg/mL (<140 pmol/L) are simultaneously measured will be considered confirmatory.

Section 4.5 Procedures for Subject Follow-up*Original text:*

As described in Section 4.4, subjects who permanently discontinue investigational product will be asked to attend the clinic as soon as possible. They will continue in the study for follow-up. They will be asked to return to clinic according to the 8 monthly visit schedule and in addition be contacted by telephone at a time corresponding to the 4-monthly visit they would have otherwise made to replenish study medication supply. If instead of these interim telephone contacts the subject prefers to attend clinic every 4 months as originally scheduled that is an acceptable alternative.

Amended text:

As described in Section 4.4, subjects who permanently discontinue investigational product will be asked to attend the clinic as soon as possible. They will continue in the study for follow-up. ***Five weeks (± 1 week) after discontinuation of investigational product, subjects will be contacted for a follow-up by telephone.*** They will be asked to return to clinic according to the 8 monthly visit schedule and in addition be contacted by telephone at a time corresponding to the 4-monthly visit they would have otherwise made to replenish study medication supply. If instead of these interim telephone contacts the subject prefers to attend clinic every 4 months as originally scheduled that is an acceptable alternative.

Table 1 Time and Events Table

Original text:

| Procedures ^{1,2} | Screening ² | Randomization ³ /Baseline (can be same day as Screening Visit) | Study Drug Check Phone Call (4-6 wks post and.) | Clinic Visit Month 4 ± 18 days then every 8 months ± 18 days throughout the study | Unscheduled dose adjustment visit (if warranted) | Clinic Visit Month 8 ± 18 days then every 8 months ± 18 days throughout the study | Final study clinic visit ⁴ (or early withdrawal) | Post-Study Follow up Phone Call 5 ± 1 weeks after last IP dose |
|---|------------------------|---|---|---|--|---|---|---|
| SAEs, AEs of special interest, AEs leading to IP discontinuation | | X | X | X | | X | X | X |

1. Subjects who discontinue investigational product should be handled as described in Section 4.4.

11. Study drug dispensing not performed at final visit, compliance check not performed at Screening.

Amended text:

| Procedures ^{1,2} | Screening ³ | Randomization ³ /Baseline (can be same day as Screening Visit) | Study Drug Check Phone Call (4-6 wks post rand.) | Clinic Visit Month 4 ± 18 days then every 8 months ± 18 days throughout the study | Unscheduled dose adjustment visit (if warranted) | Clinic Visit Month 8 ± 18 days then every 8 months ± 18 days throughout the study | Final study clinic visit ⁴ (or early withdrawal) | Post-Study Follow up Phone Call 5 ± 1 weeks after last IP dose |
|---|------------------------|---|--|---|--|---|---|--|
| SAEs, AEs of special interest, AEs leading to IP discontinuation | | X | X | X | X | X | X | X |

1. Subjects who discontinue investigational product should be handled as described in Section 4.4 **and Section 4.5**.

11. Study drug dispensing not performed at final visit, compliance check not performed at **Randomisation**.

Section 6.2.1 Cardiovascular Events

Original text:

The CEC will review and adjudicate the following clinical events:

- Myocardial infarction
- Stroke
- Unstable angina requiring revascularization
- Hospitalization for heart failure
- Sudden cardiac death
- TIA
- In addition, all clinical events submitted for adjudication and all other SAEs with a fatal outcome will be reviewed and adjudicated to classify the cause of death as cardiovascular or non-cardiovascular.

Amended text:

The CEC will review and adjudicate the following clinical events:

- Myocardial infarction
- Stroke
- ***Unstable angina requiring hospitalization***
- Hospitalization for heart failure
- Sudden cardiac death
- TIA
- In addition, all clinical events submitted for adjudication and all other SAEs with a fatal outcome will be reviewed and adjudicated to classify the cause of death as cardiovascular or non-cardiovascular.

Appendix 8 – Country Specific Requirements

Appendix 8 added (not in original text). This is a blank page headed “11.8. Appendix 8: Country Specific Requirements” to serve as a placeholder to be replaced by each participating GSK Country Medical Department with the appropriate text upon receipt of the protocol and before they distribute it further within their country.

11.9.2. Changes Resulting from Protocol Amendment 2

This amendment is applicable to all participating countries (with the exception of item 8 below which is specific to Mexico).

Summary of Changes

1. Amendment to indicate that the study should be considered Phase III in countries where albiglutide has not been granted marketing authorisation and Phase IV in countries where it has been.
2. Update to list of protocol authors.
3. Update to Sponsor Medical Monitor Contact Information.
4. Correction of terminology in Treatment Assignment section.
5. Removal of discrepancy between inclusion criterion 4 which wrongly indicates a negative **serum** pregnancy test is required to exclude pregnancy and the Time & Event table (Section 6), Section 6.2.6 Clinical Laboratory Assessments, the model consent form and the Study Reference Manual (which all correctly indicate that the requirement is for a negative **urine** test).
6. Time and Event Table 1 re-formatted as some investigators had found it confusing.
7. Addition of a Time and Event table of assessments to be performed for patients permanently discontinuing IP (Table 2). The visits and telephone contact to be performed for patients discontinuing IP had been described in text previously but an additional tabular format was recommended to aid investigators.
8. Mexican Ministry of Health requirement to report events referred to CEC by Mexican investigators to also be reported to the Ministry as SAEs.
9. Addition of requirement to record lipid results if they are available from subjects' routine clinical care outside of the trial.
10. Clarify that TRIM-D should not be assessed at Baseline in subjects whose diabetes is treated by diet and exercise alone.
11. Corrections to Data Analysis and Statistical Considerations Section to make it more terminologically correct.
12. Simplification of description of information in Section 8.3.6.4 Other Safety Analyses to properly reflect the planned reports.
13. Correction of typographical error in spelling of spermicide.
14. Correction of recipient of faxed SAE reports if the electronic CRF is unavailable.

List of Specific Changes

Title Page

Original text:

Development Phase: IV

Amended text:

Development Phase: **III/IV**

Original text:

Author (s): The protocol was developed by the members of the Executive Committee in conjunction with Duke Clinical Research Institute and the Sponsor.

The following individuals provided substantial input during protocol development:

Non-sponsor: PPD [redacted] (Executive Committee Co-Chair);
PPD [redacted] (Executive Committee Co-Chair); PPD [redacted]

Sponsor: PPD [redacted]
PPD [redacted]

Amended text:

Author (s): The protocol was developed by the members of the Executive Committee in conjunction with Duke Clinical Research Institute and the Sponsor.

The following individuals provided substantial input during protocol development:

Non-sponsor: PPD [redacted]
PPD [redacted] (Executive Committee Co-Chair); PPD [redacted]
PPD [redacted] (Executive Committee Co-Chair); PPD [redacted]

Sponsor: PPD [redacted]
PPD [redacted]

Sponsor Information Page, Sponsor Medical Monitor Contact Information

Original text:

Sponsor Medical Monitor Contact Information:

[name] [redacted]
[name]
[name]

[name]

Email: PPD [redacted]

Fax: PPD [redacted]

Telephone number: Office: PPD [redacted]

Cell: PPD [redacted]

Out of hours: PPD [redacted]

Amended text:

Sponsor Medical Monitor Contact Information:

[name] [redacted]

[name]

[name]

[name]

Email: PPD [redacted]

Fax: PPD [redacted]

Telephone number: Office: PPD [redacted]

Cell: PPD [redacted]

Out of hours: PPD [redacted]

List of Abbreviations

Original text:

Did not include the abbreviations added in amendment.

Amended text:

| | |
|------|--------------------------------------|
| HDLc | high density lipoprotein cholesterol |
| LDLc | low density lipoprotein cholesterol |
| Tg | triglycerides |
| TC | total cholesterol |

Section 3.1 Overall Design, first paragraph

Original text:

This is a Phase IV, randomised, double blind, parallel-group, placebo-controlled, multicentre study.

Amended text:

This is a ~~Phase IV~~, randomised, double blind, parallel-group, placebo-controlled, multicentre study. ***In countries where marketing authorization has been granted to albiglutide for the treatment of type 2 diabetes it is classified as a Phase IV study, elsewhere it should be considered to be a Phase III study.***

Section 4.1 Inclusion Criteria; criterion 4, first sentence

Original text:

Female: subject is eligible to participate if she is not pregnant (as confirmed by a negative serum human chorionic gonadotrophin (hCG) test for females of reproductive potential only), not breastfeeding, and at least one of the following conditions applies:

Amended text:

Female: subject is eligible to participate if she is not pregnant (as confirmed by a negative ~~serum~~ ***urine*** human chorionic gonadotrophin (hCG) test for females of reproductive potential only), not breastfeeding, and at least one of the following conditions applies:

Section 5.2 Treatment Assignment; final paragraph

Original text:

Blinded study centre personnel will receive a randomisation notification indicating only the unique subject identifier and the date and time of randomisation. Each subject number will be a unique identifier. Once a subject number has been assigned, the number will not be reused even if the subject withdraws before receiving any investigational product. Details of the treatment assignment process are contained in the SRM.

Amended text:

Blinded study centre personnel will receive a randomisation notification indicating ~~only~~ the unique subject identifier (***randomisation number***) and the date and time of

randomisation. Each **randomisation** subject number will be a unique identifier. Once a **randomisation** subject number has been assigned, the number will not be reused even if the subject withdraws before receiving any investigational product. Details of the treatment assignment process are contained in the SRM.

Table 1 Time and Events Table*Original text:*

| Procedures ^{1,2} | Screening ³ | Randomization ³ /Baseline (can be same day as Screening Visit) | Study Drug Check Phone Call (4-6 wks post rand.) | Clinic Visit Month 4 ± 18 days then every 8 months ± 18 days throughout the study | Unscheduled dose adjustment visit (if warranted) | Clinic Visit Month 8 ± 18 days then every 8 months ± 18 days throughout the study | Final study clinic visit ⁴ (or early withdrawal) | Follow up Phone Call 5 ± 1 weeks after last IP dose |
|--|------------------------|---|--|---|--|---|---|---|
| Written informed consent | X | | | | | | | |
| Review of Inc/excl criteria | X | X | | | | | | |
| Demography & directed medical history | X | | | | | | | |
| Assessment of MACE and micro-vascular events | | | | X | | X | X | |
| HbA1c | X ⁵ | | | X | | X | X | |
| Serum creatinine (eGFR) | X ⁵ | | | | | X | X | |
| Liver Function Tests ⁶ | | X | | | | X | X | |
| Genetic sampling ⁷ | | X | | | | | | |
| Patient reported outcomes questionnaires ⁸ | | X | | | | X | X | |
| Key concomitant non-diabetes medication | | X | | X | | X | X | X |
| Diabetes medication | | X | | X | | X | X | X |
| Study drug reminder | | | X | X | X | X | | |
| Physical examination ⁹ | | X | | | | X | X | |
| SAEs, AEs of special interest, AEs leading to IP discontinuation | | X | X | X | X | X | X | X |
| Pregnancy test ¹⁰ | X | X | | | | | | |
| Study drug dispense/compliance ¹¹ | | X | | X | X | X | X | |

- Subjects who discontinue investigational product should be handled as described in Section 4.4 and Section 4.5.
- Assessments per the Month 4 visit will alternate with those per the Month 8 visit throughout the study i.e., assessments at months 4, 12, 20 etc will be per Month 4; those at month 8, 16, 24 etc..will be per Month 8.
- Screening and Randomisation can occur at the same visit if all eligibility information is available. If Screening and Randomisation occur at the same visit assessments should not be duplicated.
- Once it is projected that the target number of MACE events will have been collected, a 3 month window will be defined for conducting the final, face to face visit.
- HbA1c and creatinine assessed using local laboratories at Screening visit and measured no more than 6 months prior to randomisation. If HbA1c or creatinine have not been assessed in the previous 6 months assessments to be performed via a central laboratory and results available prior to randomization. The investigator has the discretion to repeat

- screening HbA1c, and/or creatinine, based on clinical rationale even if previously available local results meet the eligibility criteria to allow the investigator to accommodate the possibility of change between screening and randomisation.
6. Liver function tests: ALT, AST, alkaline phosphatase, bilirubin, GGT. Blood samples for LFTs at randomization must be collected prior to the first dose of investigational product.
 7. Informed consent for genetic research must be obtained before collecting a sample. Genetics sample can be collected at any time after genetic consent has been obtained and the subject has been randomised.
 8. TRIM-D, EQ-5D and study specific questionnaire (details in Section 6.3).
 9. See Section 6.2.7.
 10. Only applies to women of child bearing potential. At screening perform urine pregnancy test. If positive, send serum sample to the central laboratory for confirmation. At Randomisation perform a urine pregnancy test. If result is positive do not randomize the subject. If the urine pregnancy test is negative then the subject can be randomised. If Screening and Randomisation are to take place at the same visit then follow the instructions for Screening. See Section 6.2.6.
 11. Study drug dispensing not performed at final visit, compliance check not performed at Randomisation

Amended text:

| Procedures ^{1,2} | Screening ³ | Randomization ³ /Baseline (can be same day as Screening Visit) | Study Drug Check Phone Call (4-6 wks post rand.) | Clinic Visit Month 4 ± 18 days then every 4 months ± 18 days throughout the study | Unscheduled dose adjustment visit (if warranted) | Clinic Visit Month 8 ± 18 days then every 8 months ± 18 days throughout the study | Final study clinic visit ⁴ (or early withdrawal) | Follow up Phone Call 5 ± 1 weeks after last IP dose |
|---|------------------------|--|--|--|---|--|--|---|
| Written informed consent | X | | | | | | | |
| Review of Inc/excl criteria | X | X | | | | | | |
| Demography & directed medical history | X | | | | | | | |
| Assessment of MACE and micro-vascular events | | | | X | | X | X | |
| HbA1c | X ⁵ | | | X | | X | X | |
| Serum creatinine (eGFR) | X ⁵ | | | X (alternate visits) 2 | | X | X | |
| Liver Function Tests (LFTs) ⁶ | | X | | X (alternate visits) 2 | | X | X | |
| Record available information on most recent lipid assessment⁷ | | X | | X (annually) | | | X | |
| Genetic sampling ^{7,8} | | X | | | | | | |
| Patient reported outcomes questionnaires ^{8,9} | | X ¹⁰ | | X (alternate visits) 2 | | X | X | |
| Key concomitant non-diabetes medication | | X | | X | | X | X | X |

| Procedures ^{1,2} | Screening ³ | Randomization ³ /Baseline (can be same day as Screening Visit) | Study Drug Check Phone Call (4-6 wks post rand.) | Clinic Visit Month 4 ± 18 days then every 8 4 months ± 18 days throughout the study | Unscheduled dose adjustment visit (if warranted) | Clinic Visit Month 8 ± 18 days then every 8 months ± 18 days throughout the study | Final study clinic visit ⁴ (or early withdrawal) | Follow up Phone Call 5 ± 1 weeks after last IP dose |
|---|------------------------|--|--|--|---|--|--|---|
| Diabetes medication | | X | | X | | X | X | X |
| Study drug reminder | | | X | X | X | X | | |
| Physical examination ^{9,11} | | X | | X (alternate visits) 2 | | X | X | |
| SAEs, AEs of special interest, AEs leading to IP discontinuation | | X | X | X | X | X | X | X |
| Pregnancy test ^{10,12} | X | X | | | | | | |
| Study drug dispense/compliance ^{11,13} | | X | | X | X | X | X | |

- Subjects who discontinue investigational product should be handled as described in Section 4.4 and Section 4.5 **and in Table 2.**
- ~~Assessments per the Month 4 visit will alternate with those per the Month 8 visit throughout the study i.e., assessments at months 4, 12, 20 etc will be per Month 4; those at month 8, 16, 24 etc. will be per Month 8.~~ **Assessments at month 8, 16, 24 etc. will include patient reported outcomes questionnaires, serum creatinine (eGFR), liver function tests and physical examination. Those at months 4, 12, 20 etc do not.**
- Screening and Randomisation can occur at the same visit if all eligibility information is available. If Screening and Randomisation occur at the same visit assessments should not be duplicated.
- Once it is projected that the target number of MACE events will have been collected, a 3 month window will be defined for conducting the final, face to face visit.
- HbA1c and creatinine assessed using local laboratories at Screening visit and measured no more than 6 months prior to randomisation. If HbA1c or creatinine have not been assessed in the previous 6 months assessments to be performed via a central laboratory and results available prior to randomization. The investigator has the discretion to repeat screening HbA1c, and/or creatinine, based on clinical rationale even if previously available local results meet the eligibility criteria to allow the investigator to accommodate the possibility of change between screening and randomisation.
- Liver function tests: ALT, AST, alkaline phosphatase, bilirubin, GGT. Blood samples for LFTs at randomization must be collected prior to the first dose of investigational product.
- Lipid values (TC, LDLc, HDLc, Tg) to be recorded as available from routine clinical care at baseline and annually thereafter. If results are unavailable, lipid tests are not to be performed for the study.**
- Informed consent for genetic research must be obtained before collecting a sample. ~~Genetics sample~~ **This** can be collected at any time after genetic consent has been obtained and ~~the subject has been randomised~~ **randomisation has occurred.**
- TRIM-D, EQ-5D and study specific questionnaire (details in Section 6.3).
- TRIM-D is not required for subjects whose diabetes is treated by diet and exercise alone at Baseline.
- See Section 6.2.7.
- Only applies to women of child bearing potential. At screening perform urine pregnancy test. If positive, send serum sample to the central laboratory for confirmation. At Randomisation perform a urine pregnancy test. If result is positive do not randomize the subject. If the urine pregnancy test is negative then the subject can be randomised. If Screening and Randomisation are to take place at the same visit then follow the instructions for Screening. See Section 6.2.6.
- Study drug dispensing not performed at final visit, compliance check not performed at Randomisation

Section 6 Study Assessments and Procedures; insertion of the following table after Table 1

Table 7 Time and Events Table for Subjects Who Permanently Discontinue IP Prior to the End of the Study

| Procedures | Clinic visit as soon after permanent discontinuation of IP as possible | Phone Call 5 ± 1 week after last IP dose | Continue contact schedule established at randomisation 4 monthly ± 1 month. Telephone ^{1,2} | Continue contact schedule established at randomisation 4 monthly ± 1 month. Clinic visit ^{1,3} | Final study clinic visit ⁴ |
|---|--|--|--|---|---------------------------------------|
| Assessment of MACE and micro-vascular events | X | | X | X | X |
| HbA1c | X | | | X | X |
| Serum creatinine (eGFR) | X | | | X | X |
| Liver Function Tests (LFTs) ⁵ | X | | | X | X |
| Record available information on most recent lipid assessment ⁶ | X | | X (annually) | X (annually) | X |
| Patient reported outcomes questionnaire ⁷ | X | | | | |
| Key concomitant non-diabetes medication | X | X | X | X | X |
| Diabetes medication | X | X | X | X | X |
| Physical examination ⁸ | X | | | X | X |
| AEs leading to IP discontinuation | X | | | | |
| SAEs, AEs of special interest, | X | X | X | X | X |
| Study drug compliance | X | | | | |

1. After subjects permanently discontinue IP, follow-up should continue on the 4-monthly schedule established at randomisation.
2. Where a subject would have been scheduled to attend clinic at months 4, 12, 20, 28 etc after randomisation, a telephone contact will be performed instead (with assessments as shown above).
